#### Side effects

Protocol
HypErpolarised Xenon PuLmonary MRI in the Evaluation for EndobronChial Lung
Volume Reduction Therapy
CI: [name]

IRAS ID: 346681

Xenon has been found to be extremely safe and well tolerated. Common side effects include dizziness, drowsiness, deepening of the voice and a feeling of euphoria. They typically last less than a minute. In studies of over 1000 patients performed around the world; no serious adverse events (SAEs) have been reported related to xenon inhalation.

### CT chest scan (5 mins) – not necessarily performed at baseline visit

An initial CT scan would be undertaken to clinically assess for the suitability of EBV and would ideally be used as the baseline scan. However, a research scan may be conducted, in case a new respiratory condition has developed before the baseline data collection. This will then be used as a baseline scan for the study. This is to ensure the lung parenchyma has not changed, for accurate correlation with HPX-MRI. This scan would be conducted only after the research clinician has justified it as necessary. Another research specific scan at visit 2 will be undertaken if not already done as a part of clinical reasons. The research scans would be done with a 1 litre bag of air (inspiration only).

### Pulmonary Function Tests (PFTs) – Required for eligibility assessment at baseline

This will be performed as part of the clinical work-up and the results will be recorded for this study as part of research data collection. PFTs include: Spirometry (pre- and post-BD FEV1 and FVC), lung volumes (RV and TLC) and gas transfer (TLCO and KCO). This may be repeated at follow-up visit if not already performed as part of clinical follow-up.

#### QCT (StratX) - not performed as part of research. Required for eligibility assessment.

This will be performed as part of the clinical work-up. Thin section volumetric CT chest images will be uploaded onto StratX, and its automated analysis will provide data on lung voxel density and FCS. The results will be recorded for this study as part of research data collection.

### **Chartis** – not performed at baseline visit. Required for eligibility assessment.

This will be performed as part of the clinical work-up. The endobronchial catheter-based system will measure the airflow and resistance of the occluded airway for at least 5 minutes to determine the presence of CV. The results will be recorded for this study as part of research data collection.

## 9.7. Baseline and follow up assessments

#### Initial patient approach

- Eligibility assessment by clinical team
- Study information provided to eligible patients

#### Visit 1 - Baseline

- Review of eligibility with participant
- Obtain written informed consent (unless obtained prior to baseline visit)

Protocol IRAS ID: 346681
HypErpolarised Xenon PuLmonary MRI in the Evaluation for EndobronChial Lung REC Ref:

All procedures will be performed as listed above

# Visit 2 (6 months follow-up following EBV treatment (Cohort A) or the baseline visit (Cohort B))

Participants will be invited to attend for follow up where all assessments from visit 1 will be repeated.

Face to face visits will take approximately 2 hours.

### 9.8. Sample Handling

Samples for routine clinical care will be conducted as per local hospital practice.

### 9.9. Early Discontinuation/Withdrawal of Participants

During the course of the study, a participant may choose to withdraw early from the study treatment at any time. This may happen for several reasons, including but not limited to:

- The occurrence of what the participant perceives as an intolerable AE
- Inability to comply with study procedures
- Participant decision

According to the design of the study, participants have the following options if they withdraw from the study:

- Participants can withdraw from the study but permit data obtained up until the point of withdrawal to be retained for use in the study analysis. No further data would be collected after withdrawal.
- 2. Participants can withdraw from study scans but continue with data collection. Data already obtained will be retained for use in study analysis.
- 3. Participants are free to request all data to be withdrawn at any point and not used in data analysis unless already done so prior to patient's withdrawal

In addition, the Investigator may discontinue a participant from the study at any time if the Investigator considers it necessary for any reason including, but not limited to:

- 1. Pregnancy
- 2. Ineligibility (either arising during the study or retrospectively having been overlooked at screening)
- 3. Clinical decision

Participants that choose to withdraw from the study will not be replaced. The type of withdrawal and reason for withdrawal will be recorded in the case report form (CRF). If the participant is withdrawn due to an adverse event, the Investigator will arrange for follow-up visits or telephone calls until the adverse event has resolved or stabilised.

**Protocol** 

IRAS ID: 346681

REC Ref:

#### 9.10. Definition of End of Study

The end of study will be defined as when all data has been entered and all queries resolved.

#### 10. SAFETY REPORTING

#### 10.1. Definition of Serious Adverse Events

A serious adverse event is any untoward medical occurrence that:

- results in death
- is life-threatening
- requires inpatient hospitalisation or prolongation of existing hospitalisation
- results in persistent or significant disability/incapacity
- consists of a congenital anomaly or birth defect.

Other 'important medical events' may also be considered a serious adverse event when, based upon appropriate medical judgement, the event may jeopardise the participant and may require medical or surgical intervention to prevent one of the outcomes listed above.

NOTE: The term "life-threatening" in the definition of "serious" refers to an event in which the participant was at risk of death at the time of the event; it does not refer to an event which hypothetically might have caused death if it were more severe.

#### 10.2. Reporting Procedures for Serious Adverse Events

A SAE occurring to a participant should be reported to the REC that gave a favourable opinion of the study where in the opinion of the Chief Investigator the event was 'related' (resulted from administration of any of the research procedures) and 'unexpected' in relation to those procedures. Reports of related and unexpected SAEs should be submitted within 15 working days of the Chief Investigator becoming aware of the event, using the HRA report of serious adverse event form (see HRA website). However, CT and Xenon MRI are widely used, and we have established data on safety, therefore SAEs or related AEs are not expected.

#### 11. STATISTICS AND ANALYSIS

### 11.1. Statistical Analysis Plan (SAP)

The plan for the statistical analysis of the study is outlined below. There is not a separate SAP document in use for the trial.

#### 11.2. Description of the Statistical Methods

All baseline characteristics and measures will be summarised overall and by cohort and group, using appropriate summary statistics.

ProtocolIRAS ID: 346681HypErpolarised Xenon PuLmonary MRI in the Evaluation for EndobronChial LungREC Ref:

Volume Reduction Therapy CI: [name]

We will aim to describe the prevalence of DV in patients with COPD being worked up for EBV. We will aim to describe the patterns of ventilation seen on HPX-MRI in patients with COPD who have been successfully treated with EBV and compare these findings with those who have not been successfully treated with EBV and those who have not been treated with EBV.

We will aim to examine the relationship between the presence of DV on HPX-MRI and EBV treatment success. We will also aim to correlate the presence of DV seen on HPX-MRI to the presence of CV following Chartis assessment and FC <95% on StratX. Where possible, we aim to examine the relevance of MRI perfusion to the success of EBV treatment and presence of DV. We will also aim to describe the physiological changes observed on HPX-MRI in those who have undergone EBV treatment and whether these changes are different in those who have been treated successfully to those who have not.

Continuous data, including questionnaire outcomes, will be summarised by group and time point using mean and standard deviation (or median and interquartile range if non normally distributed). Effects on outcomes over time (baseline visit and follow up visit) will be analysed using appropriate statistical models.

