**REC Ref:** 

To identify potential CV which would cause EBV treatment to fail, interlobar fissure completeness (FC) using QCT analysis and bronchoscopic assessment using a catheter-based system called Chartis is performed prior to treatment.  Chartis is performed using a catheter with an inflatable balloon at the distal tip to occlude the main lobar airway. This is connected to a console that measures airflow, pressure and resistance across the catheter.26 Once the target bronchus is occluded, absence of flow after 5 minutes signifies the absence of CV. Chartis has a proven 75 -90% accuracy prediction rate in EBV-treatment response when it determines there is no CV. 27-29 QCT analysis utilises specific automated software to measure FC based on high resolution CT (HRCT) images. The Chartis system is recommended in those with partial FC (80 – 95%) to bolster the confidence of CV assessment but is optional in those with >95% of FC and EBVtreatment is not advocated in those with incomplete fissures (<80%). 24,31

When treated with EBV, approximately 50% of patients achieved the target of ≥15% post-BD FEV₁ increase, 84% achieved the target total lung volume reduction (TLVR) of ≥350mL and 48% achieved the target mMRC dyspnoea score improvement. As not all patients with confirmed negative CV will benefit from the EBV therapy, it is important to ensure that patients are carefully selected for the procedure. Table 1 summarises the current recommendations for patient selection.

Table 1 – Current recommendations for suitability of EBV therapy 			
Criterion	Details		
Symptom limitation	mMRC ≥ 2, 6MWD between 100 – 500m.		
Residual volume >175% predicted and RV/TLC >55%	Thresholds set in line with previous trials.		
Post-BD FEV1 of 15 - 50% of predicted	Thresholds set in line with previous trials.		
No evidence of significant coexistent pulmonary pathology on HRCT	Reversible pathologies should be treated pre-EBV treatment. Exclude in severe bronchiectasis and pulmonary fibrosis. High risk of pneumothorax if bulla present in or adjacent to the target lobe.		
Heterogeneity of disease	Perfusion scan recommended in homogenous disease to target the lobe with low perfusion for EBV treatment.		
Absence of CV in the EBV-targeted lobe	QCT measurement for FC +/- Chartis system.		
Prior surgery	Exclude if prior surgery in ipsilateral lung		

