Hypercapnia	Exclude unless stable on NIV treatment for at least 3 months		
Clinically stable disease	Exclude if >3 COPD exacerbations requiring hospitalisation despite optimal medical management in the past 12 months		
Suitability for sedation or general anaesthesia and bronchoscopy	Exclude in untreated significant cardiovascular diseases or high risk of complications from general anaesthesia		

Protocol

HypErpolarised Xenon PuLmonary MRI in the Evaluation for EndobronChial Lung Volume Reduction Therapy

CI: [name]

Smoking cessation	To eliminate a contributing factor to disease		
	progression		
Undergone pulmonary rehabilitation and receiving guideline pharmacologic therapy	To optimise medical treatment prior to invasive therapy		
Severe congestive heart failure (left ventricular ejection fraction <40%) or pulmonary hypertension (right ventricular systolic pressure >50 mmHg)	Exclude due to poor outcomes		

Unfortunately, the modalities currently used to assess CV may fail. FC measurements can be under- or overestimated between software used in QCT analysis. The Chartis system may also fail in about 20% of cases. Failure has been attributed to low patient tolerance during bronchoscopy, inaccurate position or inadequate inflation of the balloon, the presence of secretions and false negative measurements.

Because of its 20% failure rate, plus the need for bronchoscopy, a technique that reduces the failure rate and removes the need for bronchoscopy would clearly be of benefit. Hyperpolarised xenon-129 (Xe) is a state-of-the-art, non-invasive, ionising-radiation-free functional imaging modality that is reproducible, quantitative, safe and well-tolerated which involves minimal patient effort. The inhalation of Xe gas imaged using MRI (HPX-MRI) enables direct visualisation of lung structure as it flows and fills the airways and alveoli, mirroring the passage of atmospheric gases. Abnormalities in ventilation, due to airway narrowing or bullae formation for example, can be qualitatively and quantitatively measured. The process of the pro

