### Cohort A (No evidence of CV and planned for EBV treatment)

- Data from this cohort will provide information on the patterns of ventilation when no CV has been established using QCT and/or Chartis assessment.
- Subgroup analysis will help identify if there are differences in the patterns of ventilation in those with confirmed successful treatment with EBV (radiologically confirmed atelectasis, and/or lung function and/or symptomatic improvement) and those who are deemed to not have successful treatment with EBV.
- Subgroup analysis will help identify if there were differences in the patterns of ventilation in those who have CV ruled out using QCT assessment only and those who have CV ruled out using both QCT and Chartis assessments.

Cohort B (Ineligible for EBV treatment following current gold standard assessments)

 Data from this cohort will provide information on the patterns of ventilation when CV has been established using current standard assessments and those deemed ineligible for EBV treatment due to inconclusive or incomplete Chartis assessment.

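### Section 11.2 analyses valve response only as a success label and never relates HPX-MRI to the size of the lung-function change, although that change is recorded

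*Protocol*

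**What the plan says.** Section 11.2 sets out the link between imaging and valve outcome in one sentence: "We will aim to examine the relationship between the presence of DV on HPX-MRI and EBV treatment success". The other outcome comparisons in that section (ventilation patterns, MRI perfusion, HPX-MRI changes after valves) also use success or no success. Section 8.1 describes success as "radiologically confirmed atelectasis, and/or lung function and/or symptomatic improvement".

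The data behind the label are numerical. Section 9.6.3 states: "PFTs include: Spirometry (pre- and post-BD FEV1 and FVC), lung volumes (RV and TLC) and gas transfer (TLCO and KCO". These tests belong to the baseline work-up and are due again at the 6-month visit if not already done clinically (Appendix A). Section 11.2 gives continuous data this role: "Continuous data, including questionnaire outcomes, will be summarised by group and time point using mean and standard deviation". It then adds a general sentence on modelling effects over time.

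Section 5 calls HPX-MRI a "functional imaging modality that is reproducible, quantitative, safe and well-tolerated" and says that ventilation abnormalities "can be qualitatively and quantitatively measured". The primary outcome in Section 6 allows quantitative or qualitative differences in ventilation pattern, including between successfully and unsuccessfully treated patients. Section 11.1 says that no separate SAP is in use, so Section 11 is the whole analysis plan.

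**The concern.** The lay summary gives the aim as learning whether ventilation patterns predict the success of valve treatment. At most about 20 patients will be treated. A yes/no label treats a patient just over a threshold like one far beyond it. In a sample this small that can hide a real graded relation, and the pilot could report no link between DV and response when one exists. It would also leave the next study without an estimate of how much RV or FEV1 differs with DV. This holds however well success and DV are defined.

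**Working it through.** **The plan's own figures.** No power or effect size is given for this relationship, so only the numbers of patients can be reproduced. Section 11.3: 60% of 20 = 12 and 50% of 30 = 15 recruits a year. Over 1.5 years that is 18 to 22.5, which agrees with 20 in Cohort A. The expected number with DV/CV is 40 × 0.5 = 20, which also agrees.

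**Inputs.**
- Treated patients: n = 20 (Section 11.3). n = 15 is also shown, because Section 11.7 uses complete cases.
- DV prevalence: 50%. Section 11.3 says more than half of patients with severe COPD. Cohort A is selected for no evidence of CV, so 20% is also shown as an assumption.
- Success rate: about 50% (the FEV1 target in Section 5) or 84% (the volume target there: "84% achieved the target total lung volume reduction (TLVR) of ≥350mL").
- Assumptions not in the protocol: a graded, bivariate-normal relation with correlation ρ, DV going with poorer response, and a two-sided 5% level.

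**Information kept by a cut (small-effect approximation).** A cut that puts a proportion p on one side keeps φ(z_p)² / [p(1 − p)].
- p = 0.50: 0.399² / 0.25 = 0.637
- p = 0.84: 0.243² / 0.134 = 0.440
- Response cut, MRI left continuous: 20 patients count as 20 × 0.637 = 12.7 at 50% success, or 20 × 0.440 = 8.8 at 84%.
- Both cut, DV 50%: 20 × 0.637 × 0.637 = 8.1, or 20 × 0.637 × 0.440 = 5.6.

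**Power by simulation, n = 20, DV 50%, success 50%.**

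| ρ | Both continuous | One side cut | Both cut, chi-square | Both cut, Fisher |
|---|---|---|---|---|
| 0.3 | 26% | 17% | 13% | 7% |
| 0.5 | 65% | 43% | 31% | 19% |
| 0.6 | 84% | 62% | 46% | 30% |
| 0.7 | 96% | 80% | 62% | 45% |

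At even splits the one-side-cut column holds whichever side is cut. Spearman correlation in place of Pearson gives about 76% at ρ = 0.6.

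**Other settings at ρ = 0.6.**

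| Setting | Both continuous | DV cut, response continuous | MRI continuous, success cut | Chi-square | Fisher |
|---|---|---|---|---|---|
| n = 20, DV 50%, success 84% | 83% | 61% | 42% | 23% | 11% |
| n = 20, DV 20%, success 50% | 83% | 46% | 61% | 29% | 17% |
| n = 15, DV 50%, success 50% | 70% | 47% | 47% | 33% | 27% |

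These are unadjusted comparisons. Baseline adjustment would alter them by an amount the protocol gives no data to estimate.

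**The opposite mechanism.** Suppose DV acts only through whether the lobe collapses. Assume 20% collapse with DV and 80% without, DV in half the patients, DV extent skewed and unrelated to response beyond presence, and success meaning collapse. With n = 20 the yes/no table then has 67% (Fisher) to 81% (chi-square) power. Correlating DV extent with response gives 21 to 45% under one set of assumptions and 35 to 55% under another.

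**Precision.** For an observed correlation of 0.6 with n = 20, Fisher's z is 0.693 with standard error 1/√17 = 0.243. The 95% limits are 0.693 ± 0.475, or 0.21 to 0.82 on the correlation scale.

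**The case against.** The strongest reply is that nothing is fixed that could lose power. Section 11.2 names no test, Section 11.6 fixes no level, and Section 11.3 describes an exploratory pilot with no power claim. All of that is correct. Section 6 also allows a quantitative MRI comparison between successful and unsuccessful patients, so the imaging side need not be binary. This narrows the point to the response side, where no sentence offers an alternative to the success label. The sentence on modelling effects over time covers change between visits, not its relation to DV.

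Second, the gain depends on the model. Section 5 explains that collateral ventilation stops the treated lobe from collapsing, which is close to all-or-none, and atelectasis is one of the named success components. Under that mechanism the yes/no table can beat a regression on DV extent. This stands, and is why the table should be kept.

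Third, the protocol names no percentage of lobar volume with DV. Its remark on quantitative measurement concerns ventilation abnormalities in general, and Section 12.2 treats matching of MRI to CT as work still being improved. A fix must therefore not depend on such a measure. Comparing the continuous response between DV present and absent does not.

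A reader might infer that the protocol commits its key test to a 2×2 table and so loses most of its power. The documents do not support that: the relationship is not called the key test, and by chi-square at even splits the relative power loss is 21 to 52% for ρ from 0.3 to 0.8.

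**Conclusion.** The point holds in a limited form. The plan records RV and FEV1 as numbers before and after treatment but relates HPX-MRI only to a yes/no response. Under a graded relation with ρ = 0.6, n = 20 and even splits, keeping the response continuous raises power from 30–46% to about 62% with DV still present/absent. With a quantitative MRI measure as well, it is about 84%. Even with MRI continuous, cutting the response discards about 36% of the information at 50% success (1 − 0.637) and 56% at 84% (1 − 0.440).

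The correlation, the 5% level, normality and Cohort A's DV prevalence are assumptions, and under all-or-none collapse the ranking can reverse. The evidence therefore supports adding a continuous-response analysis, not replacing the table. Even the better analysis would be imprecise with 20 patients, so its value lies in the estimate and interval. It should be added because it is cheap and uses data already planned.

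**What to change.** Add to Section 11.2, for example: *In patients treated with EBV, 6-month RV will be regressed on baseline DV, adjusted for baseline RV, and the estimate reported with its 95% CI. The same model for post-bronchodilator FEV1 is supportive. DV will enter as present/absent and, where the HPX-MRI analysis yields one, also as a quantitative DV or ventilation measure named before the outcome data are examined. For the quantitative measure, Spearman correlation with the 6-month change is a sensitivity analysis. DV present/absent will also be cross-tabulated against EBV treatment success.*

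The sponsor should choose the quantitative measure, since the protocol does not define one for DV.

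Cost: wording in Section 11.2 and one additional analysis, with no new patients, visits or tests. A difference in RV is less immediately clinical than a responder rate, which is a further reason to report the table alongside it.

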### 3. SYNOPSIS

In this study, we aim to identify and characterise the pattern of ventilation in 2 groups of patients with COPD using hyperpolarised xenon-129 MRI (HPX-MRI): A) patients who have been selected and subsequently undergone lung volume reduction therapy using endobronchial valves (EBV), B) those who have been identified as not eligible for endobronchial lung volume reduction therapy using current selection criteria. We also aim to assess and describe the physiological changes following endobronchial lung volume reduction therapy.

Study Title	Hyp E rpolarised X enon P u L monary MR I in the Evaluation for Endobron C hial Lung Volume Reduct I on T herapy (EXPLICIT)			
Internal ref. no. / short title	EXPLICIT			
Study registration	This study will be re	gistered on the ISRCTN		
Sponsor	Oxford University Hospitals NHS Foundation Trust [name] . Email: [contact]			
Funder	Medical Research Cou	uncil (MRC)		
Study Design	Feasibility/pilot			
Study Participants	Up to 40 patients			
Sample Size	Cohort A – up to 20 patients Cohort B – up to 20 patients			
Planned Study Period	Up to 24 months			
Planned Recruitment period	Aug 2025 – Feb 2027			
	Objectives Outcome Measures Timepoint(s)			
Primary	To characterise the pattern of ventilation on HPX-MRI in those with confirmed CV	Quantitative and/or qualitative detection of differences in the pattern of ventilation in the two cohorts being investigated:	Baseline and follow-up	

Protocol

IRAS ID: 346681 REC Ref:

HypErpolarised Xenon PuLmonary MRI in the Evaluation for EndobronChial Lung

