**Volume Reduction Therapy** 

	and those treated with EBV	,	Those with and without confirmed CV; Those who were and weren't successfully treated with EBV.	
Secondary	To describe the physiological changes of the lungs seen on HPX-MRI post-EBV treatment	a)	Quantitative and/or qualitative differences of HPX-MRI findings pre- and post-EBV therapy	Baseline and follow-up
Intervention(s)	Not applicable			
Comparator	Not applicable			_

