Proof of principle for the ability of hyperpolarised gas MRI to directly visualise CV was first described by Marshall *et al.* Using a static imaging technique of a single breath-hold of up to 20 seconds, they were able to demonstrate delayed filling of ventilation defects thought to be due to collateral ventilation in four out of 10 COPD patients scanned. Delayed ventilation (DV) could be attributed to other factors such as air trapping and significant peripheral airway obstruction. However, in their cohort of patients, collateral ventilation was more plausible due to the peripheral to central pattern of delayed filling of ventilation defects. Chen *et al.* was able to assess DV using dynamic HPX-MRI in 13 out of 15 COPD scanned and suggested further research to establish dynamic HPX-MRI ability to assess CV.

The aim of this study would be to assess the movement of Xe gas in the lungs using HPX-MRI to determine whether in patients with severe COPD it can reliably detect and measure collateral ventilation.

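### The plan correlates delayed ventilation with collateral ventilation, but the aim in section 5 is reliable detection, and no measure of how often HPX-MRI is right is planned

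*Protocol*

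**What the plan says.** Protocol section 5 (Background and rationale) closes by giving the aim: to assess xenon movement on HPX-MRI and "determine whether in patients with severe COPD it can reliably detect and measure collateral ventilation". The formal primary objective in sections 3 and 6 is descriptive: "To characterise the pattern of ventilation on HPX-MRI in those with confirmed CV" and in those treated with valves. Part (a) of the primary outcome looks for differences in ventilation pattern by CV status: "Those with and without confirmed CV".

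Section 11.2 lists several analyses by intention. The one that sets the MRI finding against the CV assessments is to "correlate the presence of DV seen on HPX-MRI to the presence of CV following Chartis assessment" and to fissure completeness below 95% on StratX. It names no coefficient, test or null hypothesis. Sensitivity, specificity, predictive value, agreement and their intervals appear nowhere in the protocol.

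Section 11.1 states: "There is not a separate SAP document in use for the trial". Section 11 is therefore the whole statistical plan. Section 11.3 calls the study an exploratory pilot of 40 patients, 20 per cohort, and section 11.6 leaves the significance level open.

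**The concern.** Whether a test reliably detects a condition is a question about individual patients: how often DV is seen when CV is present, and how often it is absent when CV is absent. A correlation between two yes/no findings answers a different question, namely whether they occur together more often than chance would give. Part (a) of the primary outcome does not fill the gap, because a difference in pattern between groups is also not an error rate.

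This matters because section 5 motivates HPX-MRI as a way to avoid bronchoscopy. For that use, the error rates in each direction are what a reader needs. Section 5 also names a way the test could go wrong: DV may come from air trapping or peripheral airway obstruction, not from CV. That would show as poor specificity, and a correlation can look respectable while specificity is poor.

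**Working it through.** **The plan's own figure.** Section 11.3 expects at least 20 of 40 patients to have DV/CV, from a prevalence above 50%: 40 × 0.50 = 20. This reproduces. The protocol gives no power figure or accuracy target to reproduce.

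**Inputs.** 40 patients, 20 per cohort (section 11.3). Assumed, because the protocol does not fix them: 20 CV-positive and 20 CV-negative patients (10 and 15 CV-positive also tried), two-sided alpha 0.05 (0.10 and 0.01 also tried), and true sensitivity and specificity from 0.60/0.60 to 0.75/0.75, plus 0.90/0.50. The number who are CV-positive may fall below 20, because section 8.1 also places patients with inconclusive or incomplete Chartis in Cohort B.

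**Step 1: one correlation, opposite error patterns.** For a 2×2 table with 20 per group, let a and b be the numbers with DV among CV-positive and CV-negative patients. Then phi = [a(20 − b) − (20 − a)b] / √[20 × 20 × (a + b) × (40 − a − b)].

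- Sensitivity 18/20, specificity 10/20 (a = 18, b = 10): (180 − 20)/√(400 × 28 × 12) = 160/366.6 = 0.44.
- Sensitivity 10/20, specificity 18/20 (a = 10, b = 2): (180 − 20)/√(400 × 12 × 28) = 0.44.

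The first test wrongly flags half of the CV-negative patients. The second misses half of the CV-positive patients. The coefficient cannot tell them apart, even when it is reported only descriptively.

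**Step 2: chance of a significant association.** Take a ~ Binomial(n₁, sensitivity) and b ~ Binomial(n₂, 1 − specificity), and sum the probabilities of all tables with a/n₁ > b/n₂ and p ≤ alpha.

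| Sens / spec | CV+ / CV− | Alpha | Fisher | Pearson |
|---|---|---|---|---|
| 0.60 / 0.60 | 20 / 20 | 0.05 | 14% | 22% |
| 0.65 / 0.65 | 20 / 20 | 0.05 | 34% | 45% |
| 0.70 / 0.70 | 20 / 20 | 0.05 | 60% | 71% |
| 0.75 / 0.75 | 20 / 20 | 0.05 | 83% | 90% |
| 0.90 / 0.50 | 20 / 20 | 0.05 | 74% | 84% |
| 0.70 / 0.70 | 15 / 20 | 0.05 | 63% | 67% |
| 0.70 / 0.70 | 10 / 20 | 0.05 | 45% | 58% |
| 0.70 / 0.70 | 20 / 20 | 0.10 | 71% | 81% |
| 0.70 / 0.70 | 20 / 20 | 0.01 | 37% | 48% |

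**Step 3: one concrete result.** Suppose 14/20 are correct in each group, so a = 14 and b = 6. Misclassified: (6 + 6)/40 = 30%. Phi = (14 − 6)/20 = 0.40, and Fisher p = 0.026. The exact (Clopper–Pearson) 95% interval for 14/20 runs from the 2.5% point of Beta(14, 7) to the 97.5% point of Beta(15, 6), which is 46% to 88%. The association is significant, yet for sensitivity and specificity alike values below 50% are not excluded.

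**Step 4: what accuracy reporting would give.** Exact 95% intervals: 16/20 = 80% (56–94%); 18/20 = 90% (68–99%); with 15 CV-positive patients, 12/15 = 80% (52–96%).

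**The case against.** The strongest reply is that the aim in section 5 is background text. The formal objective is to characterise patterns, in an exploratory pilot that says an accurate sample size calculation is not possible, and association and description suit such a study. This stands in part: the study cannot be faulted for failing to confirm reliability. It does not explain why accuracy should go unestimated, since a pilot's estimates and their uncertainty are what the next study needs.

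A second reply is that the correlation may be reported descriptively, perhaps with a cross-table from which sensitivity and specificity follow. That is possible, but section 11.2 does not commit to it, and Step 1 shows that a coefficient alone will not do.

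Four stronger readings are tempting, and the documents do not support them:

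- A reader might infer that the correlation is the only analysis involving CV status. Part (a) of the primary outcome is another, though it is not an accuracy analysis.
- A reader might infer that the plan tests a null of no association and will treat significance as success. No test, null or success criterion is stated.
- A reader might infer that an unreliable test would usually come out positive. That fails at 0.65/0.65, at alpha 0.01, and by Fisher's test with 10 CV-positive patients.
- A reader might treat the rates in Step 2 as type I error inflated many times over 5%. That needs a threshold for reliable, such as 0.80, which the protocol never sets. The 75–90% in section 5 cannot serve, because it is the Chartis "accuracy prediction rate in EBV-treatment response when it determines there is no CV", not accuracy for detecting CV.

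**Conclusion.** The mismatch holds. Section 5 asks about reliable detection, while the planned correlation and the planned comparison by CV status both measure association or difference. Neither estimates how often HPX-MRI is right, and the protocol says no further plan is in use that could add this.

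The size depends on assumptions. With 20 CV-positive and 20 CV-negative patients and two-sided 0.05, a test that misclassifies 30% in each direction would reach significance about 60% (Fisher) to 71% (Pearson) of the time. The range drops to 34–45% at 0.65/0.65, to 37–48% at alpha 0.01, and to 45–58% with 10 CV-positive patients. So the conclusion is that association is a weak guide to accuracy here, and not that a misleading positive result is to be expected. The Step 1 result needs no assumption about alpha. The change is worth making because it uses the same data and answers the question the protocol asks.

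**What to change.** In section 11.2, replace the correlation with:

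> Sensitivity and specificity of DV on the baseline HPX-MRI will be reported with exact 95% confidence intervals, separately against CV on Chartis (in those with a conclusive Chartis result) and against FC <95% on StratX. A significant association alone will not be taken as evidence of reliable detection.

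For quantitative DV measures, report the ROC area with its 95% confidence interval.

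The two references must be kept apart because they can disagree. Under section 5, a patient with 80–95% fissure completeness goes on to Chartis and may be found free of CV, which makes that patient positive on one reference and negative on the other.

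The change needs no new data, visits or patients. Its cost is wide intervals: 16/20 gives 56–94%, so the pilot can estimate accuracy but not confirm reliability. The Chartis comparison is also likely to rest on fewer than 40 patients, since section 5 makes Chartis optional above 95% completeness and puts its failure rate at about 20%. The report should state how many patients enter each comparison.
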